4.3 Inclusion criteria

- A. Children aged ≥4 years old
- B. Meet the diagnostic criteria for ASD of the DSM-5
- C. ASD Diagnosis confirmed by the Autism Diagnostic Observation Schedule (ADOS) or Autism Diagnostic Interview, Revised (ADI-R)
- D. Provide written informed consents

4.4 Exclusion criteria

- A. With metal implants in the body
- B. History of epilepsy or other neurological disease
- C. Require surgical treatment due to structural abnormalities indicated by brain MRI
- D. With genetic or chromosomal abnormalities
- E. With psychiatric/mental disorder (e.g., very early-onset schizophrenia) other

than ASD

- F. Suffer from serious heart disease and/or severe hearing impairment
- G. Intracranial hypertension
- H. Participating in other clinical trials
- I. Participants who received other interventions within 4 weeks prior to enrollment.

4.5 Exit criteria

- A. The child had obvious side effects during the intervention
- B. Self-withdrawal (patient withdrawal of consent, etc.)
- C. Lost to visit
- D. Other reasons for the subject's inability to complete the full process of this trial (e.g., severe somatic disease were found after enrollment)

4.6 Case rejection criteria

- A. Those participants found not to meet the trail criteria after enrollment
- B. Poor compliance, do not cooperate with the protocol to complete the 5-day intervention course, etc.

5.0 Intervention

5.1 Intervention program

• Machine: Pulsed magnetic Stimulation Device (M-100 Ultimate, Shenzhen Yingchi Technology Co.,Ltd, Shenzhen, China)

2 Intervention protocol: target left M1, and details of parameter are shown below.

	Intensity	Frequency	Number of	Inter-	Number	stimulation	Inter-	Repli-	Total	total
		in the	pulses in	cluster	of inter-	time	cluster	cation	pulses	time
		cluster	the cluster	frequency	cluster		interval		number	
					pulses					
cTBS	80%MT	50HZ	3	5HZ	200	40s	0	3	1800	120s

3 Treatment period: 10 times a day, 1 hour interval, a total of 5 days

5.2 Combined treatment

The combined treatment and (or) medication during the study should be detailed in the case report form, including the name, dose, route of administration, usage, start and end time of treatment and (or) medication.

6.0 Follow-up plan

6.1 Follow-up time arrangement

- Total of three follow-up time.
- Follow-up visit 1 (V0): Baseline
- Follow-up visit 2 (V1): immediately after the 5-day intervention
- Follow-up visit 3 (V2): 4 weeks after the 5-day intervention
- **2**Unscheduled follow-up (USV): No limit on number of times

6.2 Follow-up content: Process schedule

Follow-up time	V0	V1	V 2
Follow-up content	-2w	5d	+4w
Informed consent	×		
Inclusion/exclusion criteria	×		
Demographic data	×		
History taking	×		
check-up	×		
IQ	×		
Autism Diagnostic Observation Schedule (ADOS)/	×		
Autism Diagnostic Interview, Revised (ADI-R)	^		
Childhood Autism Rating Scale (CARS)	×		×
Repetitive Behaviors Scale – Revised (RBS-R)	×	×	×
Social Responsiveness Scale (SRS)	×	×	×
Behavior Rating Inventory of Executive Function(BRIEF)	×	×	×
Conners parent symptom questionnaire (PSQ)	×	×	×
Peabody Picture Vocabulary Test (PPVT)	×		×
Chinese Communication Development Inventory (CCDI)	×		×
Multilingual Assessment Instrument for Narratives (MAIN)	×		×
Clinical Efficacy Rating Scale (CGI)		×	×
Resting-state EEG	×	×	×
Adverse event		×	

7.0 Outcome measures

7.1 Primary outcome measures:

The Social Responsiveness Scale (SRS) provides the multi-dimensional measure of social interaction allowing the rating of social impairment in ASD for children aged 4 - 18 years. It can generate a total raw score and five theoretical subscales scores (labeled social awareness, social cognition, social communication, social motivation,

Efficacy and mechanistic of repeated transcranial magnetic stimulation in children with autism spectrum disorder: an open-label clinical trial. NCT05472870

Version: 2.0/April 2, 2022

and autistic mannerisms), and higher scores indicates increased social impairment. We used SRS to monitor the response to the intervention in social domain as it's able to measure subtle changes in the severity of symptoms over time. Parents completed SRS before their child receiving the intervention, immediately after the 5-day intervention and 4 weeks after the 5-day intervention.

7.2 Secondary outcome measures:

At baseline, Post-intervention, 4-week follow-up:

- 1) Repetitive Behaviors Scale-Revised (RBS-R) is a questionnaire that is used to measure the breadth of repetitive behavior in children, adolescents, and adults with Autism Spectrum disorders. The RBS-R provides a quantitative, continuous measure of the full spectrum of repetitive behaviors. The RBS-R consists of six subscales including: Stereotyped Behavior, Self-injurious Behavior, Compulsive Behavior, Routine Behavior, Sameness Behavior, and Restricted Behavior, that have no overlap of item content. The higher scores indicating severer symptoms.
- 2) Behavior Rating Inventory of Executive Function-Parent (BRIEF-P). School Version contains eight clinical domains that can generate behavioral regulation and meta-cognition indices and an overall executive composite score; Preschool Version comprises five subscales that can yields inhibitory self-control, flexibility and emergent meta-cognition indices and an overall executive composite score), which provided an ecologically sensitive measure of executive function (EF) performance in everyday (school/home) environments.
- 3) Conners Parent Rating Scale (CPRS-48), which provides a qualitative and quantitative picture of children's emotions and behavior, based on five subscales assessing: Conduct Problems, Learning Problems, Psychosomatic, Impulsive-Hyperactive and Anxiety. And CRPS-48 allows for another factor: the Hyperactivity Index (HI), which includes the 10 items that are considered to be the most sensitive to treatment effects.

At baseline and 4-week follow-up:

- 4) Childhood Autism Rating Scale (CARS). CARS is a behaviour-rating scale used to assess the presence and severity of the symptoms of autism spectrum disorder(ASD), with scores ranging from 15 to 60 and high scores indicating severe symptoms. Change of the CARS score from baseline to 1 months after treatment to evaluate the effect of rTMS treatment on ASD.
- 5) Chinese Communicative Development Inventory (CCDI), which is a powerful tool to assess early vocabulary development and the language skills of older children with developmental disorders and the effectiveness of their interventions; raw scores were used here allowing us to analysis change in language level over time.
- 6) Peabody Picture Vocabulary Test (PPVT), one of the most commonly used assessment tests that measure understanding of single-word. The higher score of PPVT means better single-word comprehension.

At Post-intervention and 4-week follow-up:

7) Clinical Global Impression Scale (CGI, which consists of 3 items that assess global illness severity, overall improvement from the start of treatment, and

Efficacy and mechanistic of repeated transcranial magnetic stimulation in children with autism spectrum disorder: an open-label clinical trial. NCT05472870

Version: 2.0/April 2, 2022

therapeutic response(referred to as "CGI-S," "CGI-I," and "CGI-E", respectively), we use CGI-I to rate how much the patient's illness has improved or worsened relative to a baseline measurement (a seven-point scale: 1 = "very much improved" to 7 = "very much worse").

7.3 Exploratory outcome measures:

Before receiving the intervention, and 4 weeks after the end of 5-day intervention, children having certain expression ability need to complete the Multilingual Assessment Instrument for Narratives (MAIN) to assess narrative comprehension and production skills.

Resting-state EEG data will be collected before and after the intervention to investigate the effect of the intervention on brain activity.

8.0 Safety evaluation

8.1 Physical Signs

Careful physical examination of participants will be conducted by clinician at each visit, with special attention to the inquiry and checking for spasm, convulsions, scalp discomfort, local pain, headache, dizziness, tinnitus, nausea, etc.

8.2 Adverse events and incidence

A semi-structured interview was administered following each treatment session and follow-up by the rTMS technician. A standardized adverse events assessment form was completed if adverse events or physical discomfort were reported. Using this form, detailed descriptions of the adverse events experienced were recorded, including rating the event as mild (no impairment, no need stopping trial), moderate (some impairment, need stopping trial, no need for intervention), severe (evidence of impairment, need stopping trial and need for intervention).

9. 0 Adverse events and serious adverse events

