	Conners parent symptom questionnaire (PSQ), Behavior Rating						
	Inventory of Executive Function(BRIEF), Peabody Picture						
	Vocabulary Test (PPVT); Chinese Communication Development						
	Inventory (CCDI); Clinical Efficacy Rating Scale (CGI) scores.						
	Exploratory indicators are changes in resting-state						
	Electroencephalogram (EEG) characteristics before and after the						
	intervention, and Multilingual Assessment Instrument for						
	Narratives (MAIN) scores.						
Safety Evaluation	During the intervention and follow-up periods, a careful						
	physical examination will be conducted by clinician when						
	participants come to the hospital. Meanwhile, A semi-structured						

Efficacy and mechanistic of repeated transcranial magnetic stimulation in children with autism spectrum disorder: an open-label clinical trial. NCT05472870

Version: 2.0/April 2, 2022

	interview will be administered following each treatment session						
	and follow-up by the rTMS technician, special attention will be						
	paid to TMS common discomforts, such as spasms, convulsions,						
	scalp discomfort, local pain, headache, dizziness, tinnitus,						
	nausea, etc. If any adverse events or physical discomfort were						
	reported, detailed descriptions were recorded and graded						
	according to their severity.						
Inclusion criteria	A. Children aged ≥4 years old						
	B. Meet the diagnostic criteria for ASD of the DSM-5						
	C. ASD Diagnosis confirmed by the Autism Diagnostic						
	Observation Schedule (ADOS) or Autism						
	Diagnostic Interview, Revised (ADI-R)						
	D. Provide written informed consents						
Exclusion criteria	A. With metal implants in the body						
	B. History of epilepsy or other neurological disease						
	C. Require surgical treatment due to structural						
	abnormalities indicated by brain MRI						
	D. With genetic or chromosomal abnormalities						
	E. With psychiatric/mental disorder (e.g., very						
	early-onset schizophrenia) other than ASD						
	F. Suffer from serious heart disease and/or severe						
	hearing impairment						
	G. Intracranial hypertension						
	H. Participating in other clinical trials						
	I. Participants who received other interventions within						
	4 weeks prior to enrollment.						
Intervention	Participants will receive cTBS over the left M1 for 5 consecutive						
	days. The detailed parameters as follows: 80% of RMT, 60 cycles						

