9.2 Record of adverse events

Record all adverse events that occurred after signing the informed consent form. The contents of each adverse event record should include the following points:

- Duration of the adverse event : start time and end time;
- **2**Severity of adverse events:

Mild-no impairment, no need stopping trial Moderate-some impairment, need stopping trial, no need for intervention Severe-evidence of impairment, need stopping trial and need for intervention;

• Relationship between adverse events and intervention: Investigators assessed the correlation between adverse events and the intervention as: positive / likely related

/ possibly related / likely unrelated / unrelated;

4 Management of adverse events: The investigator should follow up the adverse events until the symptoms disappear or stabilize; if the adverse event remains at the end of the study, follow up again within one month after the end of the study.

The intervention used in this study is rTMS, in principle, there is no safety risk in the use of rTMS in children if the safety guidelines developed by the international expert panel are strictly adhered to. However, rTMS may bring temporary minor discomfort such as scalp discomfort, localized pain, dizziness, headache, fatigue, tinnitus, anxiety, etc., mostly relieved within 24 hours. Serious side effects of seizures and neurocardiogenic syncope induced during stimulation have also been reported, but subjects who experienced these two adverse reactions had a history of depression and/or syncope.

The intervention process of this study is conducted in the hospital, and the subjects will be closely followed and supported in case of adverse reactions; if medical treatment is needed, the pediatrician will provide the treatment plan and follow-up visits. In addition, the study will continue to follow up the adverse events within 4 weeks after the 5-day intervention.

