11.5 Statistical analysis method

Data will be preprocessed and/or analyzed using SPSS25.0, SAS9.2, Matlab, and R.

• Analysis of the primary outcome measures:

SRS scores at baseline, immediately after the end of 5-day intervention and 4 weeks after the end of 5-day intervention will be analyzed using repeated measures ANOVA.

2 Analysis of other behavioral outcome measures:

RBS-R, BRIEF, PSQ scores at baseline, immediately after the end of 5-day intervention, and 4 weeks after the end of 5-day intervention will be analyzed using repeated measures ANOVA or Friedman test.

CARS, PPVT, CCDI, MAIN scores at baseline and 4 weeks after the end of 5-day intervention will be analyzed using paired-samples t-tests or Mann-Whitney Wilcoxon test.

3 EEG analysis

EEG data will be preprocessed and analysed by MATLAB. Changes in the electrophysiologicalactivity characteristics of the brain at baseline, immediately after the end of 5-day intervention and 4 weeks after the end of 5-day intervention will be analyzed and then correlated with clinical behavioral outcome.

4 Safety evaluation

Summarize the occurrence of adverse events: summarize the number of cases,

Efficacy and mechanistic of repeated transcranial magnetic stimulation in children with autism spectrum disorder: an open-label clinical trial. NCT05472870

Version: 2.0/April 2, 2022

instances, and incidence of adverse events and list all adverse events, those related to the study intervention protocol, serious adverse events, and those leading to exit; list the number of cases, instances, and incidence of mild, moderate, and serious adverse events; give a description for adverse events related to the intervention.

SAnalysis of baseline characteristics

The analysis of baseline characteristics included: demographics (age and gender); baseline analysis of each observation used in this study.

The number of cases, mean, standard deviation, median, minimum and maximum values were calculated when the variables were quantitative indicators; the number of cases and composition ratio were calculated when the variables were categorical indicators.

12. 0 Principal Investigator and contact person

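### The adverse-event severity grades include a need to stop the trial, so an event that impairs the child without a need to stop has no grade

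*Combined protocol and SAP*

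**What the plan says.** The Study Summary (Safety Evaluation) says that for reported events "detailed descriptions were recorded and graded" by severity. Section 8.2 defines the first two grades as "mild (no impairment, no need stopping trial), moderate (some impairment, need stopping trial, no need for intervention") and the third as "severe (evidence of impairment, need stopping trial and need for intervention"). Section 9.2 repeats the scale under its severity item, for example "Moderate-some impairment, need stopping trial, no need for intervention". Neither section gives a fallback grade or a second scale.

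The scale has to cover a wide range of events. Section 9.1 counts events as adverse even when they have no link to treatment. Section 9.2 requires recording from consent and continues follow-up of events for 4 weeks after the 5-day course. The schedule in 6.2 puts the baseline visit at 2 weeks before the course.

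The grades are used in the analysis: section 11.5 will "list the number of cases, instances, and incidence of mild, moderate, and serious adverse events". It will also "list all adverse events, those related to the study intervention protocol, serious adverse events, and those leading to exit".

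**The concern.** A severity scale should place every recorded event in exactly one grade, on the basis of how bad the event was. Here each grade also carries a judgement about stopping. Mild needs both no impairment and no need to stop; moderate and severe both need impairment and a need to stop. An event that impairs the child but gives no reason to stop meets none of the three definitions. Nor does an event that calls for stopping without impairing the child, though that is less likely clinically.

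Safety of an accelerated, high-dose course in children is a stated aim (section 1.0), and the by-grade incidence in 11.5 is the planned severity summary. The trial has one arm, so no control group shows how raters apply the scale. If raters settle the unclassifiable events differently, the by-grade figures partly reflect those choices.

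**Working it through.** The plan states no figure on this point, so there is none to reproduce. The check sets the definitions against every combination they could meet.

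**Inputs (8.2, repeated in 9.2).** Three yes/no conditions: impairment (I), need to stop (S) and need for treatment (T). The plan's word for the third condition is read here as treatment of the event.
- Mild: I = no, S = no; T not mentioned.
- Moderate: I = yes, S = yes, T = no.
- Severe: I = yes, S = yes, T = yes.

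**Enumeration.** 2 × 2 × 2 = 8 combinations.

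| I | S | T | Grade as written | Grade with S removed |
|---|---|---|---|---|
| no | no | no | mild | mild |
| no | no | yes | mild | mild |
| no | yes | no | none | mild |
| no | yes | yes | none | mild |
| yes | no | no | none | moderate |
| yes | no | yes | none | severe |
| yes | yes | no | moderate | moderate |
| yes | yes | yes | severe | severe |

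**As written.** Graded: 2 mild + 1 moderate + 1 severe = 4. Ungraded: 8 − 4 = 4, of which 2 have impairment with no need to stop and 2 have a need to stop with no impairment.

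**Other readings.**
- If mild also implies no need for treatment, the second row loses its grade: 5 of 8 ungraded.
- If the two impairment phrases, for moderate and for severe, are separate levels, there are 3 × 2 × 2 = 12 combinations. Mild covers 2, moderate 1 and severe 1, so 12 − 4 = 8 are ungraded.
- If impairment always means stopping, the two rows with I = yes and S = no cannot occur: 2 of the remaining 6 are ungraded. If stopping also always means impairment, 0 of the remaining 4 are.

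**After a change.**
- Removing S from moderate and severe only: 2 of 8 stay ungraded (need to stop, no impairment).
- Removing S from all three: mild 4 + moderate 2 + severe 2 = 8, so 0 of 8 stay ungraded.

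**Where the gap could be met.** Two illustrations, not predictions: a headache during the course that impairs the child, is treated and gives no reason to stop; and an unrelated illness in the follow-up that impairs the child and is treated. Both fall in the row I = yes, S = no, T = yes.

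**Scale of one reclassification.** With the planned minimum of 30 children (4.2), moving one child from one grade to another changes each grade's incidence by 1/30 = 3.3 percentage points. The documents give no event rates, so the number of such moves cannot be estimated.

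**The case against.** The best defence is that the scale is a ladder: no impairment, continue; impairment, stop; impairment needing treatment, stop and treat. Both sections attach stopping to every impairing grade, which is implicit evidence for such a rule, and the exit criterion for side effects in 4.5 A is compatible with it. During the 5-day course this reading is plausible, and on it the two most important gaps disappear. It does not carry over to all the events that must be recorded. After the course there is no session or course left to stop; only withdrawal from follow-up remains, which would not protect the child. An unrelated illness, before or after stimulation, need not call for stopping either. No section states the rule, and 4.5 A uses a different, undefined threshold.

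The safeguards are substantial, and that part of the defence stands. Section 8.2 requires detailed descriptions on a standard form, 5.2 requires concomitant treatment to be recorded, and 11.5 lists all events, serious events and those leading to exit. With about 30 children such a listing can be read directly. Section 9.2 also expects minor effects: "rTMS may bring temporary minor discomfort such as scalp discomfort, localized pain, dizziness, headache". These fit mild.

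A reader might infer that impairing events in children who continue would be quietly called mild, so that a finding of only mild events would be true by construction. The documents do not support that. Calling such an event mild breaks the no-impairment condition; calling it moderate breaks the stopping condition. Nothing says which a rater would choose. The text also grades the need to stop, not what was done, so a rater may judge that stopping was needed even though the child continued.

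**Conclusion.** The concern holds as a defect in a stated rule. Read literally, the scale leaves 4 of 8 combinations without a grade. The count assumes that impairment, need to stop and need for treatment are separate yes/no conditions and that mild is silent on treatment. The ladder reading narrows the gap during the course but does not close it for unrelated events or follow-up events.

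The 4 of 8 are cells in a definition. They do not mean that half of the events would be ungraded: the number affected may be zero, and the direction of any error in the by-grade incidence is unknown. The method planned for the primary SRS outcome does not use the grades. The change is worth making because it is cheap and the grades feed a planned safety summary.

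**What to change.** In 8.2 and 9.2, remove the stopping condition from all three grades and keep the rest:
- mild: no impairment;
- moderate: impairment, no treatment needed;
- severe: impairment needing treatment.

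This keeps need for treatment, the only clear separator of moderate from severe in the present text.

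Record action taken as a separate field on the adverse-event form: none, session skipped, course stopped, or withdrawn from the trial. The management item in 9.2 describes follow-up ("The investigator should follow up the adverse events until the symptoms disappear or stabilize") and names no such field; the form itself is not in the documents and may already have one.

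Move the cautious link into 4.5, so that impairment during the 5-day course leads to a review of whether to stop. Without this, removing stopping from the grades would leave the undefined side-effect threshold in 4.5 A as the only stopping criterion specific to adverse effects.

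In 11.5, tabulate mild, moderate and severe events, replacing the word serious in the by-grade sentence. Report serious adverse events as defined in 9.3, and action taken, separately.

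The cost is wording in four sections and at most one form field; no visit, assessment or participant is added. The downside is that some moderate or severe events may appear among children who completed the course. For example, an impairing headache that needed treatment would count as severe.
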